**38. Section 9. DATA ANALYSIS/STATISTICAL METHODS, 9.2. Analysis of Secondary Endpoints, 2nd paragraph**

**Deletion**

~~Supportive analyses of the main efficacy endpoint will be performed in the Intent to Treat (ITT) population, consisting of all randomized subjects.~~

## 1. AMENDMENTS FROM PREVIOUS VERSION(S)

This SAP is an amendment of version 1.0.

The analysis of the global response endpoint has been clarified. Other minor changes have been made to bring the SAP in agreement with Protocol Amendment 3.

This SAP is an amendment of version 2.0. The changes have been made to bring the SAP in agreement with protocol Amendment 4. The primary changes for Protocol Amendment 4 allow enrolment of subjects with *Candida* endocarditis and *Candida* osteomyelitis.

This SAP is an amendment of version 3.0. The changes have been made to tighten up the definition of the global response endpoint.

This SAP is an amendment of version 4.0. The changes have been made to conduct additional analysis with subjects who completed study treatment.

This SAP is an amendment of version 5.0. This amendment reflects the changes that were made in protocol amendments 8 and 9, which include expansion of enrolment criteria to include infants (aged 1 month - < 2 years) who do not have microbiologically confirmed *Candida* but who are at high risk of candidiasis, analysis of pharmacokinetic parameters of polysorbate 80, and addition of an interim analysis.

## 2. INTRODUCTION

Anidulafungin is a member of the echinocandin class of antifungals and exhibits fungicidal activity against *Candida* species. In the United States, anidulafungin is approved for the treatment of candidaemia and other forms of *Candida* infections (intra-abdominal abscess and peritonitis). In Canada and Europe, anidulafungin carries a similar indication and is approved for the treatment of invasive candidiasis/candidemia in adult non-neutropenic patients. To date, there are no clinical studies evaluating anidulafungin in paediatric subjects with invasive *Candida* infection. This study will assess the pharmacokinetics, safety and efficacy of anidulafungin in subjects 1 month to <18 years of age with invasive candidiasis, including candidemia (ICC). Exposure-response relationships of anidulafungin and polysorbate 80 will also be assessed in a population pharmacokinetic-pharmacodynamic (PK-PD) analysis.

### 2.1. Study Design

This prospective, open-label, non-comparative study will assess the safety and efficacy of anidulafungin when used to treat children between the ages of 1 month and <18 years with invasive candidiasis, including candidemia (ICC).

To participate in this study, at the time of enrolment subjects must have either a confirmed diagnosis of ICC (based on the growth of *Candida* sp. from a culture obtained from a normally sterile site within 96 hours prior to enrollment), or mycological evidence highly suggestive of *Candida* sp. (eg, the growth of yeast in culture and/or the direct microscopic visualization of yeast, hyphae or pseudohyphae from a sample obtained from a normally sterile site within 96 hours prior to enrolment). Subjects may enroll and initiate study

treatment prior to culture confirmation of *Candida* sp. If culture confirmation is not obtained, subjects may remain in the study and receive study treatment at the discretion of the investigator. Should the investigator choose to withdraw the subject from study treatment, the subject will be required to return for the 2-week and 6-week follow-up visits.

In order to accelerate the availability of PK and safety data in the lowest age group (1 month to < 2 years), the study population is broadened only in this age group to include children at risk for invasive candidiasis. Thus, eligibility criteria have been modified in Amendment 9 to additionally allow enrollment of infants (aged 1 month - < 2 years) who do not have microbiologically confirmed *Candida* but who are at high risk of candidiasis, and for whom the investigator considers antifungal therapy with at least 5 days of IV anidulafungin to be appropriate.

All subjects meeting screening criteria will receive IV anidulafungin. On Day 1, subject is to receive a loading dose of 3.0 mg/kg (not to exceed 200 mg). Subject is then to receive a daily maintenance dose of 1.5 mg/kg (not to exceed 100 mg) from Day 2 onwards. Subjects will receive treatment (either solely anidulafungin, or anidulafungin followed by oral fluconazole) for a minimum duration of 14 days from the time of the last negative culture (defined as the second of two consecutive negative cultures, separated by at least 24 hours, following the last positive culture) and improvement of clinical signs and symptom of candidemia or invasive candidiasis.

Subjects without microbiologically confirmed *Candida* infection will be treated with IV anidulafungin at the discretion of the investigator to a maximum of 35 days. Subjects may be switched to oral fluconazole (6-12 mg/kg/day, maximum 800 mg/day) after at least 5 days of IV anidulafungin treatment.

In subjects with *Candida* endocarditis and *Candida* osteomyelitis who require continued treatment beyond the maximum total treatment duration (49 days), this treatment will be considered outside the context of this clinical trial and study drug will not be supplied by the Sponsor. For the purpose of study treatment evaluation, Day 35 (for subjects who require continued IV treatment) or Day 49 (for subjects who required continued oral therapy) will be considered the last day of study drug treatment. These subjects are also required to return for the 2-week and 6-week follow-up visit following the last dose of study drug.

At selected investigator sites, anidulafungin pharmacokinetics will be assessed in the first 6 subjects between 1 month to <2 years of age to confirm whether or not the recommended dosing regimen contained within the protocol for this age group is appropriate.

Efficacy will be based on a determination of global response (combination of clinical and microbiological response) of success, failure or indeterminate at the EOIVT, EOT, 2-week FU and 6-week FU visits. Rates of relapse (recurrence) and/or new infection will be assessed at the FU visits. Safety will be evaluated through assessment of adverse events and monitoring of clinical laboratory tests (hematology and serum chemistry), temperature, and physical examination results. All subjects will be followed for safety through the 6-week FU visit.

### 2.1.1. Study Drug and Dosing

This is a one arm study. All subjects meeting screening criteria will receive IV anidulafungin. On Day 1, subject is to receive a loading dose of 3.0 mg/kg (not to exceed 200 mg). Subject is then to receive a daily maintenance dose of 1.5 mg/kg (not to exceed 100 mg) from Day 2 onwards. Subjects will be stratified by age (1 month - <2 years, 2 - <5 years, and 5 - <18 years). Subjects may be switched to oral fluconazole (6-12 mg/kg/day, maximum 800 mg/day) after at least 5 days of IV treatment, provided that the pre-specified criteria are met.

### 2.1.2. Sample Size

The planned enrolment is approximately 60 evaluable subjects (those subjects who have received at least one dose of anidulafungin and have confirmed *Candida* infection).

## 2.2. Study Objectives

### Primary Objective

Objective 1: *To assess the safety and tolerability of anidulafungin when used to treat children with invasive candidiasis, including candidemia.*

This assessment will be based on the reports of adverse events throughout the study, laboratory tests, and physical examination results.

### Secondary Objectives

Objective 1: *To assess the efficacy of anidulafungin, as measured by global response, at the following time points: EOIVT, end of treatment (EOT), 2-week follow-up (FU) visit and 6-week FU visit.*

This assessment will be based on assessment of the clinical and microbiological responses categorized as one of the possible outcomes: success, failure, or indeterminate. The objective will be accomplished by presenting frequencies and percentages of global success for each time point overall and by age category (1 month - <2 years, 2 - <5 years, and 5 - <18 years).

Objective 2: *To explore pharmacokinetic parameters of anidulafungin in children aged 1 month to <2 years following IV infusion of anidulafungin (AUC24 and Cmax).*

This pharmacokinetic objective will be addressed in a separate analysis plan.

Objective 3: *To explore pharmacokinetic parameters of polysorbate 80 following IV infusion of anidulafungin (area under curve over dosing interval (AUC24) and peak concentration (Cmax).*

This pharmacokinetic/pharmacodynamic (PK-PD) objective will be addressed in a separate analysis plan.

Objective 4: *To explore the exposure-response (safety and efficacy endpoints) relationship of anidulafungin using a nonlinear mixed effects approach as appropriate, including exploring the association between PK-PD index (eg, AUC/MIC) and efficacy endpoints.*

This pharmacokinetic/pharmacodynamic (PK-PD) objective will be addressed in a separate analysis plan.

Objective 5: *To assess rates of relapse (recurrence) at the Week 2 and Week 6 FU visits.*

The objective will be accomplished by presenting the frequencies and percentages of relapse (recurrence) for each follow up visit overall and by age category (1 month - <2 years, 2 - <5 years, and 5 - <18 years).

Objective 6: *To assess rates of new infection at the Week 2 and Week 6 FU visits.*

The objective will be accomplished by presenting the frequencies and percentages of emerging infection for each follow up visit overall and by age category (1 month - <2 years, 2 - <5 years, and 5 - <18 years).

Objective 7: *To assess all-cause mortality during study therapy and FU visits.*

The objective will be accomplished by presenting the proportion of deaths due to all causes for each time point overall and by age category (1 month - <2 years, 2 - <5 years, and 5 - <18 years) at EOIVT, EOT and 2 week and 6 week follow-up visits. The mortality rates will also be described using the Kaplan-Meier methods of summarizing survival.

### **3. INTERIM ANALYSES, FINAL ANALYSES AND UNBLINDING**

#### **3.1. Interim Analyses**

Subjects will be stratified by age (1 month - <2 years, 2 - <5 years, and 5 - <18 years), allowing  $20 \pm 2$  in each stratum. An interim analysis to assess safety, PK and efficacy will be performed after approximately  $20 \pm 2$  for age cohorts 2 to <5 years and 5 to < 18 years groups have completed the study.

The details of the dissemination plan (Tables, Listings and Figures) for subpopulation (age cohorts 2 to <5 years and 5 to <18 years) documented in [Appendix 2](#).

#### **3.2. Final Analysis**

Final analysis will be conducted after the database is released.

### **4. HYPOTHESES AND DECISION RULES**

#### **4.1. Statistical Hypotheses**

As this is a descriptive study, no hypothesis testing will be performed.

## 4.2. Statistical Decision Rules

All analyses will be considered descriptive; therefore, no statistical tests of hypotheses will be performed.

## 5. ANALYSIS SETS

The main subject populations to be used for the analysis are a Modified-Intent-to-Treat (MITT) population and a safety population.

The MITT population will be the primary efficacy analysis population. The PP population will be used in additional supportive analyses of efficacy. The safety population will be used in all analyses of safety. There will be an additional PK population.

### 5.1. Modified Intent-To-Treat Analysis Set

The Modified Intent-To-Treat (MITT) population is defined to be the set of all subjects who have received at least one dose of study drug and who have a confirmed *Candida* infection. This means that the subject must have a positive culture for *Candida* sp from cultures obtained within 96 hours before study entry or at screening.

Note: Due to logistical issues at the local level and the timing of screening activities/treatment initiation, subjects whose qualifying culture for study entry was collected just outside the 96 hour window (ie, within 5 days) will be included in the MITT population.

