### Statistical Methods:

The primary analysis will be the evaluation of adverse events throughout the trial, laboratory tests, ECG findings (if applicable), temperature, and physical examination. The set of subjects for this evaluation will be the Safety population, defined as all subjects with at least 1 dose of study medication. The following parameters will be summarized: rates of

discontinuation, adverse events, and laboratory abnormalities. Safety data will be descriptively summarized. Descriptive statistics for categorical data will include frequencies and/or percentages.

Secondary efficacy analyses will be assessed in the Modified Intent-to-Treat (MITT) population, defined as all subjects who have received at least one dose of study drug and who have microbiological confirmation of *Candida* infection. The efficacy analysis will be an assessment of global response, conducted by frequencies and percentages of global response (success, failure).

Other analyses will include rates of relapse (recurrence) and new infection at FU visits, and analysis of time to death during study therapy and FU visits.

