In the event the investigator chooses to administer anidulafungin in combination with a second antifungal agent, anidulafungin will be discontinued following the obtainment of required blood samples for pharmacokinetic analysis as specified by the protocol; the data from these subjects will not be utilized for secondary efficacy endpoint analyses but will be assessed for safety. After the dosing regimen is confirmed by the Sponsor, enrollment will be opened to additional subjects within this age group at all investigator sites. Subsequent to this time point, the use of a second systemic antifungal agent (eg, amphotericin B) will not be permitted in any subject.

[figure not shown]
A population PK-PD analysis will also be performed in all other subjects enrolled and will include subjects <2 years of age who are not part of the 6 subject cohort described above, in which 3 to 5 sparse pharmacokinetic samples will be collected. Additionally, at the request of PDCO, pharmacokinetics of polysorbate 80, a solubilizing agent contained in the IV formulation of anidulafungin, will also be explored.

Efficacy will be based on a determination of global response (combination of clinical and microbiological response) of success or failure at the EOIVT, EOT, 2-week FU and 6-week FU visits. Rates of relapse (recurrence) and/or new infection will be assessed at the FU visits. Safety will be evaluated through assessment of adverse events and monitoring of clinical laboratory tests (hematology and serum chemistry), temperature, and physical examination results. All subjects will be followed for safety through the 6-week FU visit.

The planned enrolment is approximately 60 evaluable subjects (those subjects who have received at least one dose and confirmed *Candida* infection).

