### 6.2.2. Days 1 and 2 ONLY for Sub-study Subjects (first 6 subjects aged 1 month to <2 years at selected sites)

Prior to the administration of the first dose of study drug, a plasma sample (0.1 – 0.2 mL) should be obtained and sent to the reference laboratory to test for assay interference. Excess blood collected for safety laboratory testing may be used for this sample, otherwise it should be collected directly from the subject.

**Pharmacokinetic sampling:** Six (6) blood samples (0.3-0.5 ml each to provide 0.1 – 0.2 mL plasma) will be collected for anidulafungin measurement at the following time points:

- **On Day 1:** 2 minutes before the end of infusion;

- **On Day 2:** Just prior to the start of infusion; 2 minutes before the end of infusion, 6 hours after start of infusion, 12 hours after start of infusion, and 24 hours after start of infusion.
- In the event that the sample required 2 minutes before the end of infusion was not taken at the specified time, every effort must be made to acquire a sample within 5 minutes of the end of infusion with proper and specific time documentation.

Note: In case the subjects are not ready for serial pharmacokinetic sampling on this specific day, this can be re-arranged at a later date when they continue to receive 1.5 mg/kg daily maintenance dose of anidulafungin. The flexibility of the sampling time is also allowed as long as the actual time of collection is recorded in the CRF.

Ideally, the pharmacokinetic (PK) sampling would be taken from a different site/line than the one used for study drug infusion. However, at the discretion of the investigator and with appropriate flushing of the line to clear all drug residues, samples may be collected using the same line.

**\*\* Important Note \*\*** For subjects in whom the investigator has chosen to administer anidulafungin in combination with a second antifungal agent, these subjects will be discontinued from treatment following completion of pharmacokinetic sampling but will remain in the study for continued safety assessments and are required to return for the 2-week and 6-week follow-up visits.

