## 7.9. Pharmacokinetic Assessments

### 7.9.1. Blood Sampling for Subjects in the PK Sub-Study (1 Month to <2 Years of Age)

The first 6 children aged <2 years enrolled in the PK substudy (at selected centers) will undergo the PK sampling as described below.

Prior to the administration of the first dose of study drug, a plasma sample (0.1 – 0.2 mL) should be obtained and sent to the reference laboratory to test for assay interference. Excess blood collected for safety laboratory testing may be used for this sample, otherwise it should be collected directly from the subject.

Following initiation of treatment, blood samples (approximately 0.3 - 0.5 mL each) will be collected for anidulafungin measurement at the following 6 time points.

- On Day 1 (receiving 3 mg/kg IV infusion): 2 minutes before the end of infusion;
- **On Day 2 (receiving 1.5 mg/kg IV infusion):** Just prior to the start of infusion; 2 minutes before the end of infusion, 6, 12 and 24 hours after the start of infusion.

Due to the special conditions of the study population, the sampling time and day can be flexible in order to fit the subject's schedule. For instance, if serial pharmacokinetic sampling cannot be scheduled on Day 2, subjects will continue to remain on IV treatment to allow sample collection at a later date. The actual sampling time and date will be recorded in the CRF.

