## 9.2. Analysis of Secondary Endpoints

The efficacy analysis will be an assessment of global response at EOIVT, EOT, 2 week and 6 week FU visits. Global response will be derived from the investigator's assessment of clinical and microbiological response as defined in [Section 7.4](#). The analysis will be conducted by frequencies and percentages of global response by determination (success, failure). These efficacy analyses will be assessed in the Modified Intent-to-Treat (MITT) population, which will be defined as all subjects who have received at least one dose of study drug and who have microbiological confirmation of *Candida* infection.

Rates of relapse (recurrence) and new infection at FU visits will also be derived from the investigator's assessment of clinical and microbiologic response as defined in [Section 7.4](#), and analyzed. Time to death will be analyzed and all-cause mortality rates determined.

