#### **Clinical Response**

**Cure:** Resolution of sign and symptoms attributed to *Candida* infection; no additional systemic or oral antifungal treatment required to complete the course of therapy.

**Improvement:** Significant, but incomplete resolution of signs and symptoms of the *Candida* infection; no additional systemic or oral antifungal treatment required to complete the course of therapy.

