#### ***Important Notes:***

- Initiating or resuming oral antifungal therapy following EOT for prophylactic purposes is permitted, and does not reflect a requirement for additional systemic antifungal therapy for treatment purposes, and therefore does not constitute treatment failure. (Note: It must be clear in the project database that administration of additional antifungal therapy is for prophylactic purposes, otherwise it will be deemed as being administered for treatment of continued infection, in which case study drug treatment will be considered clinical failure.)
- Administration of non-absorbable antifungal agent is not considered systemic antifungal treatment in the context of this study.

**Failure:** No significant improvement in signs and symptoms, or death due to the *Candida* infection. Subjects must have received at least 3 doses of study medication to be classified as a failure.

**Indeterminate:** Evaluation cannot be made due to withdrawal from the study prior to assessment of cure or failure. Subjects who receive fewer than 3 doses of study medication will be assigned as a clinical efficacy response of indeterminate.

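### The MITT set omits the protocol's efficacy exclusion of PK sub-study infants given a second antifungal, so those infants would be counted as non-successes

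*SAP*

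**What the plan says.** Protocol section 3 (and the Study Design part of the summary) allows the six PK sub-study infants to be treated with anidulafungin alone or with a second systemic antifungal. For those given the combination, "the data from these subjects will not be utilized for secondary efficacy endpoint analyses but will be assessed for safety".

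The efficacy population is defined three times, and no definition carries that rule:

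- SAP 5.1: "the set of all subjects who have received at least one dose of study drug and who have a confirmed" *Candida* infection.
- Protocol 9.2: MITT, "which will be defined as all subjects who have received at least one dose of study drug and who have microbiological confirmation of" *Candida* infection.
- Protocol summary, Statistical Methods: "defined as all subjects who have received at least one dose of study drug and who have microbiological confirmation of" *Candida* infection.

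SAP 5.3.2 does restrict efficacy to monotherapy infants, but only for a stand-alone summary of the six. SAP 8.2 runs all efficacy analyses on MITT, with the per-protocol (PP) set as support.

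**The concern.** A culture-confirmed infant given the combination meets both MITT conditions, although the protocol bars that infant's data from the analyses MITT exists to support. Because the combination is tied to early stopping of anidulafungin and to use of another antifungal, such an infant would be classed as a non-success. The error therefore runs in one direction, and it falls entirely in the 1 month to <2 years stratum, the smallest-data group and one for which the SAP promises separate response rates.

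Two analysts could also reach different denominators. One might let the specific sentence in Protocol section 3 govern. Another might follow SAP 5.1, since Protocol section 9 allows the SAP to modify the protocol's analysis plans.

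**Working it through.** **Which response would a combination infant receive?**

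1. Protocol 6.2.2: "these subjects will be discontinued from treatment following completion of pharmacokinetic sampling". The last scheduled sample is 24 hours after the start of the Day 2 infusion, so on the default schedule anidulafungin stops after two doses.
2. SAP 6.1.1.2: "Subjects who receive fewer than 3 doses of study medication will be assigned as a clinical efficacy response of indeterminate". Global success needs cure or improvement, so this infant is not a success.
3. Sampling may be postponed; Protocol 7.9.1 says "subjects will continue to remain on IV treatment to allow sample collection at a later date". Three or more doses are then possible. Cure and improvement in SAP 6.1.1.2 still carry the condition "no additional systemic or oral antifungal treatment required to complete the course of therapy", which an infant treated with a second antifungal would not ordinarily meet.
4. SAP 6.1.4 sets global response to failure after two or more days of another antifungal during treatment, whatever the reason, provided the clinical team identifies it as active against the baseline species. It makes no exception for the permitted combination.
5. The sensitivity analysis in SAP 8.2.2 removes indeterminate and missing responses but keeps failures. Whether it reveals the problem depends on the label.
6. The PP set (SAP 5.3.1) does not reliably remove these infants. Its concomitant-antifungal criterion covers prohibited therapy only, and its duration criteria are waived for failures.

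**Size.** The plan has no calculated figure to reproduce: Protocol 9.4 states that no sample size calculation was made. The only check available is 3 strata × 20 = 60, which matches the planned number.

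Inputs:

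- *n* = 20 in the stratum (the 20 ± 2 enrolment allowance in Protocol section 3, taken here as the MITT number) and 60 overall.
- *p* = success among the other subjects, assumed 75.6% from the adult trial in Protocol 1.3.2, with 60% and 85% as a range.
- *c* = culture-confirmed combination infants, 0 to 6; not stated in either document.

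Rate if excluded = *p*. Rate if kept as non-successes = *p* × (*n* − *c*)/*n*. Fall = *p* × *c*/*n*.

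| *c* | Stratum rate if kept (*n* = 20, *p* = 75.6%) | Fall in stratum | Fall overall (*n* = 60) |
|---|---|---|---|
| 0 | 75.6% | 0 | 0 |
| 1 | 75.6 × 19/20 = 71.8% | 3.8 points | 1.3 points |
| 3 | 75.6 × 17/20 = 64.3% | 11.3 points | 3.8 points |
| 6 | 75.6 × 14/20 = 52.9% | 22.7 points | 7.6 points |

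Varying the assumptions at *c* = 3:

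- *p* = 60%: 60 × 3/20 = 9.0 points. *p* = 85%: 85 × 3/20 = 12.8 points.
- *n* = 18: 75.6 × 3/18 = 12.6 points. *n* = 22: 75.6 × 3/22 = 10.3 points.

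Whole-number example with the SAP's exact (Clopper-Pearson) 95% interval, *c* = 3: 13/17 = 76.5% (50.1 to 93.2) if excluded, 13/20 = 65.0% (40.8 to 84.6) if kept.

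Sensitivity analysis at *c* = 3: 75.6% if the three are labelled indeterminate and dropped, 64.3% if labelled failure and retained.

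Relapse, new infection and mortality change only through the denominator and any events in these infants. Two relapses, for example, read 2/20 = 10.0% instead of 2/17 = 11.8%.

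**The case against.** The best counter-argument is that the rule exists and only a cross-reference is missing. The protocol's specific sentence can be read as qualifying its general MITT definition. SAP 5.3.2 speaks of pooling the six infants' data for safety and mentions efficacy only for monotherapy infants, so the authors' intent looks clear. That is fair as to intent, but none of it removes anyone from MITT, and SAP 5.1 is the text a programmer would implement.

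Non-success is also not certain on every route. Clinical response is the investigator's judgement. With three or more doses, the label depends on how the no-additional-antifungal condition is read and on what the clinical team identifies under SAP 6.1.4. For endocarditis and osteomyelitis, Protocol 7.4.2 puts no such condition on improvement. This stands as a narrow qualification: on the default two-dose schedule the indeterminate label is automatic.

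The size is uncertain too. The combination was optional, at-risk infants without confirmed *Candida* never enter MITT, and *c* may be 0. The infant MITT may also be smaller than 20, because the stratum can now include unconfirmed infants; that would enlarge the effect of each combination infant.

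Finally, the study is descriptive, with no hypothesis tests, and the two intervals in the example overlap widely. That limits the seriousness but does not justify reporting a rate on a population the protocol rules out.

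**Conclusion.** The concern holds. As written, the MITT definitions produce an efficacy population that contradicts the protocol's own exclusion, and the affected infants would be classed as indeterminate or failure, apart from the narrow routes noted above. On the stated assumptions (20 infants in MITT, 75.6% success in the rest), the youngest stratum's rate is understated by 3.8 to 22.7 points for one to six affected infants, and the overall rate by 1.3 to 7.6 points. The effect is zero if no culture-confirmed infant received the combination.

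The consequence is confined to secondary, descriptive endpoints. The primary safety analysis and the interim analysis of the two older cohorts are not affected. It should be fixed, but it does not threaten the trial's main conclusion.

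**What to change.** Add a sentence to SAP 5.1 stating that PK sub-study subjects who received a second systemic antifungal in combination with anidulafungin are excluded from MITT, and therefore from PP, while monotherapy sub-study subjects with confirmed *Candida* remain. No separate PP exclusion or exemption in SAP 6.1.4 is then needed.

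Report the number removed in the table of exclusions from MITT that SAP Appendix 2 already lists for the interim, and carry that table into the final analysis. State also whether these infants count toward the 60 evaluable subjects, since Protocol 9.4 and SAP 2.1.2 define evaluable by the same two conditions.

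The same sentence should be added to Protocol 9.2 and the protocol summary so that the documents agree. A protocol change needs ethics committee approval (Protocol 12.1), so this can wait for the next amendment; the SAP sentence is enough to settle the analysis.

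The cost is one SAP sentence before database release, and up to six fewer infants in the efficacy set, which the protocol already requires.
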